5.5 Independent Review

All statistical analyses for primary reporting of trial results will be independently verified through dual programming. Two statisticians will each program all datasets and analyses for the DSMB reports and the primary manuscript(s) and the results will be compared.

6 INTERIM ANALYSES

6.1 Frequency of and Timepoints for Interim Analysis

DSMB meetings to review safety data are as desired by the DSMB, as described in the DSMB charter. No interim efficacy analyses are planned for this trial.

In addition to the indicated interim safety analyses, the DSMB may request additional safety and efficacy analyses at their discretion.

6.2 Stopping Rules for Interim Efficacy Analysis

We do not anticipate applying formal stopping rules for either efficacy or futility in this trial. However, we will include feasibility evaluations to allow us to determine when the first wave of COVID-19 has resolved, such that further enrollment in the trial is unlikely. Given the totality of the evidence and enrollment in the trial to date, a decision may be made to suspend or terminate the trial if there is clear evidence that the first wave is over in Utah.

6.3 Blinding in the Interim Analysis

The closed-session DSMB reports will present generic treatment designations (e.g., “A” and “B”) to promote objective decisions regarding study procedures and analyses. Nonetheless, the DSMB retains the prerogative to request precise treatment designations rather than generic labels.

7 PLANNED ANALYSES

7.1 Description of Subject Characteristics

The primary results will include key baseline characteristics for the ITT population, overall and by assigned arm. A partial list of these characteristics includes

- age
- sex
- race
- ethnicity.

The primary results will also include a CONSORT-like diagram describing patient flow. This diagram or its footnotes will depict, at minimum, counts in the SCREEN, ELIGIBLE, CONSENTED, ITT, dITT, SAFETY, and PP populations along with frequencies for categories describing why unretained patients were not part of subsequent subsets.

7.2 Primary Outcome Analysis

Due to the nature of the data collected over the $DayR$ –($DayR+14$) interval, and uncertainty about the distribution of shedding duration and the resulting hazard function, our primary analysis will apply the stratified log-rank test to compare the distribution of shedding duration between the hydroxychloroquine and control groups, with administrative right censoring at $DayR+14$. The primary analysis will be conducted using a 2-sided $\alpha=0.05$. The log-rank test will be stratified by the age group randomization stratum. The Efron approach will be

used to account for tied shedding duration times. Kaplan-Meier curves will summarize the shedding time distributions in the two randomized groups.

The primary analysis of shedding duration will consider every hospitalized day as having a positive swab result. See section 5.4.

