5.6 Household Contacts

Household contacts 18 years or older will be asked to self-collect oral swabs in the same manner and same daily schedule as the study participant. Provision of the oral swabs will be considered implied consent, waiving the need for consent documentation.

5.7 Data collection.

Research coordinators and/or investigators will collect data and record them on paper and/or electronic CRF provided by the Data Coordinating Center (DCC). Data quality will be monitored by clinical data managers at the DCC. Note that given concerns for contagion during the pandemic, coordinators will practice “no-touch” practices for data collection and entry.

6.0 Analysis and interpretation of data.

A formal statistical analysis plan (SAP) will be written and finalized before the conclusion of enrollment and prior to the beginning of data analysis. The principles of this SAP are outlined here.

We note that in the unique circumstances of this trial setting, it is possible that information may become available that would lead to modifications of prespecified analysis. A hypothetical example would be evidence from multiple global studies that a particular underlying condition is strongly associated with outcomes such as shedding or hospitalization rates in response to hydroxychloroquine. In such circumstances, a modification to this study's analysis plan could

UTAH One (Understanding Treatment And Health in the Ongoing coroNa Epidemic): A Hydrochloroquine Outpatient Study

be considered, if possible with the investigators blinded to the effect of the modification on the analysis, and in consultation with the DSMB. If the statistical analysis plan were to be modified, the analytic plan would be updated, with the previous version retained, and the modification explicitly noted in the presentation of the trial results.

The primary prespecified analysis for efficacy is a comparison of duration of viral shedding during the first 14 days after randomization between the two treatment arms. For each participant, this outcome will be defined as the number of days until an oral swab sample shows no shedding, as confirmed by a sample from the subsequent day. Thus, for example, a participant with their first negative samples on days 7 and 8 would be treated as having stopped shedding on Day 7. The requirement for confirmation will be waived for patients who are negative for shedding on Day 14.

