Due to the nature of the data collected over a 14-day interval, and uncertainty about the distribution of shedding duration and the resulting hazard function, our primary analysis will apply the stratified log-rank test to compare the distribution of shedding duration between the hydroxychloroquine and control groups, with administrative right censoring at day 14. The primary analysis will be conducted using a 2-sided $\alpha=0.05$. The log-rank test will be stratified by the age group randomization stratum. The Efron approach will be used to account for tied shedding duration times. Kaplan-Meier curves will summarize the shedding time distributions in the two randomized groups.

Special handling will be required in our primary analysis of shedding duration for periods in which patients are hospitalized because swabs will not be obtained during hospitalizations. In our primary analysis, we will apply a last value carried forward imputation approach during hospitalization, and assume continued viral shedding during hospitalizations for patients whose last pre-hospitalization assessment is positive. A sensitivity analysis will right censor follow-up on the day of hospital admission. These two analyses represent the range of plausible scenarios for shedding during hospitalization under the assumption that any association between hospitalization and shedding must be positive; i.e., conditional on past history, the risk of viral shedding on any given day is at least as large for hospitalized as for non-hospitalized patients. We expect a relatively small proportion of subjects to be hospitalized, limiting the impact of assumptions concerning shedding during hospitalizations on the primary analysis. Additional sensitivity analyses, including analyses in which the end date of shedding is modeled as a latent variable will be considered.

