- Cover page: Added approval date for SAP Version 1.3 and creation date for SAP Version 1.4.
- Edited the handling of swabs on a hospitalized day, which affects the primary outcome. Background: The protocol had assumed swabs would not be collected during hospitalization and prescribed last value carried forward (LVCF), explicitly noting that positive swab results would be assumed during hospitalization if the last pre-hospitalization swab were positive. The SAP had noted swabs may not be collected during hospitalization and also specified LVCF imputation. Discussion with the statistical team

after the primary manuscript had been drafted revealed differences of interpretation among the statistical team as to the intent of the protocol (and SAP) language, but with the expectation that results would be qualitatively similar with various reasonable interpretations because of the small percentage of hospitalized participants and given the swab data available from these participants. The statistical team decided after extensive debate that all hospitalized days would be considered as having a positive swab, even if there were no swab or a negative swab on such a day, and considered this consistent with the original intent of the protocol and the convention already in the SAP that on days with mixed swab results, a positive swab would supersede a negative swab. Thus, a hospitalization's assumed positive swab results would supersede any obtained swabs those days. The edits to the SAP are tracked below.

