Primary Outcome Duration of viral shedding (through 14 days after randomization, i.e., *DayR* $+ 14$): this is an integer outcome which is defined as (Date of first sustained negative swab (ignoring any swab that was not in the interval *DayR* $+ 1$ through *DayR* $+ 14$, inclusive) - *DayR*). The date of first sustained negative swab is the first day with a negative swab followed by the next available day's swab being negative. The requirement for confirmation will be waived for patients who are negative for shedding on *DayR* $+ 14$. If no more positive swabs nor negative swabs are available by *DayR* $+ 14$ following a negative swab, the date of the negative swab will be considered confirmed for the primary analysis (using the last-observation-carried-forward approach). If the final swab from on or before *DayR* $+ 14$ which has a positive or negative result is positive and there were not two preceding consecutive negative swabs, the duration will be considered to be right censored on the day of the positive swab.

The primary outcome was viral-shedding duration over the first two weeks. Because the protocol stipulated that swabs would not be obtained during hospitalizations, and that positive results would be carried forward through hospitalization, swab status was considered positive for all hospital days. Hospitalizations or swabs documented after day 15 (i.e., *DayR* $+ 14$) were not used for this outcome. Duration was considered to end on the first day of two consecutive negative swabs, allowing days without swab results between two negative swabs, or on the last available swab result if negative. Without negative confirmation, the outcome was considered right-censored on the day of their last positive result or day 15. In a sensitivity analysis, we treated hospitalized patients prior to day 15 without a prior confirmed

negative as right-censored on the day of hospital admission or day 15.

Also of note is that we assumed all participants were positive on the day of randomization, even if a negative swab were available. It was uncommon for a swab to be available on the day of randomization.

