7.2.1 Additional Analyses of Primary Outcome

A sensitivity analysis will right-censor follow-up on the day of hospital admission. These two analyses (primary and sensitivity) represent the range of plausible scenarios for shedding during hospitalization under the assumption that any association between hospitalization and shedding must be positive; i.e., conditional on past history, the risk of viral shedding on any given day is at least as large for hospitalized as for non-hospitalized subjects. It is expected that a relatively modest proportion of subjects will be hospitalized, limiting the impact of assumptions concerning shedding during hospitalizations on the primary analysis. Additional sensitivity analyses, including analyses in which the end date of shedding is modeled as a latent variable will be considered.

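### SAP 5.4 derives scoring every hospital day swab-positive from the protocol, but the protocol specifies last value carried forward, and no committed analysis shows the primary result under that wording

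*SAP*

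**What the plan says.** - **Protocol 6.0, hospital days.** The primary analysis uses LVCF during hospitalization and will "assume continued viral shedding during hospitalizations for patients whose last pre-hospitalization assessment is positive". A sensitivity analysis censors at admission.
- **Protocol 6.0, endpoint.** Shedding ends at the first negative swab "as confirmed by a sample from the subsequent day".
- **SAP 7.2.** "The primary analysis of shedding duration will consider every hospitalized day as having a positive swab result".
- **SAP 5.4, reason for the rule.** It cites two protocol premises, that swabs would not be taken in hospital and that positives would be carried forward. The sentence ends: "positive results would be carried forward through hospitalization, swab status was considered positive for all hospital days".
- **SAP 5.4, confirmation.** The next available negative confirms, "allowing days without swab results between two negative swabs". A last negative with no later result also counts as confirmed.
- **SAP 7.2.1.** It commits to censoring at admission. Beyond that: "Additional sensitivity analyses, including analyses in which the end date of shedding is modeled as a latent variable will be considered".
- **SAP change log, version 1.4.** Discussion "after the primary manuscript had been drafted revealed differences of interpretation among the statistical team". The team decided that hospital days count as positive even where a negative swab was obtained that day, and judged this consistent with the protocol's intent.
- **Protocol 6.0, changes to the plan.** The previous version is to be retained and "the modification explicitly noted in the presentation of the trial results".

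**The concern.** LVCF carries the last value whatever it is. The protocol's sentence about assumed shedding is conditional on a positive last swab, and the condition has meaning only if a last negative is treated differently. SAP 5.4 repeats the positive half, omits the negative half, and draws a conclusion covering all hospital days. A reader of SAP 5.4 alone would take the rule in use to be the one prespecified.

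What is at stake is mainly transparency about the primary endpoint. For an affected participant, the SAP rule moves the end of shedding later or turns an event into a censored time. LVCF was not kept as a sensitivity analysis when it was replaced, so a reader cannot compare the result under the protocol's wording with the result used. The change came after the manuscript was drafted, which makes that comparison more useful. Describing the rule as following from the protocol also makes it easier to overlook the note that Protocol 6.0 requires.

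**Working it through.** **1. Where the rules can differ.** Days are counted from randomization. Each cell gives the event day unless marked as censored.

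| Swabs and stay | SAP primary | LVCF, carried negative confirms | Hospital days as no result, SAP 5.4 gap rule | Only an actual next-day swab confirms | Censor at admission |
|---|---|---|---|---|---|
| A. Positive 1–5, hospital 6–10, negative 11–14 | 11 | 11 | 11 | 11 | censored 6 |
| B. Positive 1–3, negative 4–5, hospital 6–10, negative 11–14 | 4 | 4 | 4 | 4 | 4 |
| C. Positive 1–4, negative 5, hospital 6–10, negative 11–14 | 11 | 5 | 5 | 11 | censored 6 |
| D. As C, but positive on 11 and negative 12–14 | 12 | 5 | 12 | 12 | censored 6 |
| E. Positive 1–4, negative 5, hospital 6–14 | censored 14 | 5 | 5 | no confirmed event | censored 6 |

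Rows A and B show agreement when the last pre-admission swab is positive or a negative is already confirmed. Rows C to E start from a single unconfirmed negative, and there the answer depends on the confirmation convention. In row C, two of the three conventions give day 5, a date that neither committed SAP analysis produces.

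One further route is a negative swab actually obtained in hospital. Take positive 1–5, hospital 6–9, real negatives on 7–9 and negatives afterwards. Using the obtained swabs gives day 7; the SAP primary gives day 10.

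**2. Bound on power.** The documents give no hospitalization rate and say only that it should be small. Assume 2% to 10% hospitalized, of whom 10% to 30% enter with a single negative:

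- Low end: 400 × 0.02 × 0.10 = 0.8 participants.
- High end: 400 × 0.10 × 0.30 = 12 participants.

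Protocol Table 2 reproduces first. At a 50% event rate there are 200 events, and exp[(1.960 + 0.842)/√(200/4)] = 1.486, which rounds to the stated 1.49. Power at 1.49 is Φ[ln(1.49) × √(200/4) − 1.96] = Φ(0.86) = 0.805. If all 12 lost their event, leaving 188, it is Φ[ln(1.49) × √(188/4) − 1.96] = Φ(0.77) = 0.78. That is about 2.5 points at the extreme of the assumed range.

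**3. Effect on the test.** This simulation compares the SAP primary with LVCF in which a carried-forward negative confirms. The 200 per arm (Protocol 2.7), the 14 days and the age-stratified log-rank test come from the documents. The rest is assumed: daily clearance hazard 0.09, admission day uniform on 2–10, 5-day stay, daily swabs outside hospital, age strata 60/25/12/3%, single-swab false-negative rate 5% or 20%, no treatment effect, 4,000 replicates per scenario. Paired figures are for the two false-negative rates.

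| Hospitalized by arm | Participants changed | Mean shift in Z | Significance at 0.05 changes |
|---|---|---|---|
| Admission unrelated to shedding | | | |
| 5% / 5% | 1.8; 3.0 | 0.00; 0.00 | 0.60%; 1.07% |
| 2% / 6% | 1.5; 2.4 | 0.035; 0.078 | 0.62%; 0.92% |
| 3% / 10% | 2.4; 3.9 | 0.064; 0.135 | 1.18%; 1.88% |
| Admission only while shedding | | | |
| 5% / 5% | 0.9; 3.1 | 0.00; 0.00 | 0.70%; 1.55% |
| 2% / 6% | 0.8; 2.5 | 0.027; 0.099 | 0.40%; 1.80% |
| 3% / 10% | 1.3; 4.1 | 0.049; 0.168 | 1.00%; 2.50% |

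The shift is toward longer shedding in the arm with more admissions. In at least 30% of changed participants the overridden negative was a false negative, and in all of them if only people still shedding are admitted.

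**The case against.** The strongest reply is that the protocol requires confirmation by a sample from the next day. An imputed value is not a sample, and Protocol 6.0 nowhere says that a carried-forward negative confirms. On that reading row C gives day 11 under both rules. This stands, and it is why the difference must be stated conditionally. It would be tempting to say that the protocol itself dates cessation at day 5; the documents do not support that. Row D shows the cost of that convention, since a participant with a positive swab on day 11 is scored as cleared on day 5. However, the SAP does not apply the strict reading elsewhere: it accepts the next available swab, allows gaps, and accepts a last single negative.

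The protocol also lends the team's reading some support. It says that the primary and censoring analyses span the plausible range if shedding in hospital is at least as likely as outside. Carrying a negative through the stay falls below that floor. Protocol 6.0 likewise treats hospitalized participants as symptomatic on each hospital day. This supports all-positive as a reasonable choice. It does not remove the LVCF wording or its condition.

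It is also true that SAP 5.4 does not literally say the protocol required every hospital day to be positive. It cites two premises that are in the protocol; the fault is that its conclusion does not follow from them.

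Finally, the log discloses the change, its timing and the disagreement, and records an expectation of qualitatively similar results. A reader might infer from the timing that results drove the choice. Nothing in the documents shows that.

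**Conclusion.** The point holds as a minor one. SAP 5.4 derives an unconditional rule for the primary endpoint from a conditional protocol rule, and no committed analysis uses the protocol's literal LVCF wording. The conflict lies between the current Protocol 6.0 and the current SAP 5.4, 7.2 and 7.2.1; the change log supplies only the timing, intent and reach of the rule.

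The difference is confined to participants admitted after a single unconfirmed negative, subject to the confirmation convention, or with negative swabs obtained in hospital. The simulation covers only the first group. There, 0.8 to 4.1 participants per trial change outcome, the mean Z shift is at most 0.17, and significance changes in 0.4% to 2.5% of trials. These sizes rest on assumed hospitalization, clearance and swab-error rates and on the convention that a carried-forward negative confirms.

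A reader might conclude that the SAP primary is wrong and should be replaced. That does not follow: it is defensible, particularly where negatives before admission are often false. Nor does Protocol 6.0 require the rule to be labelled post hoc; it requires the modification to be explicitly noted. Whether a publication did so cannot be seen from these documents.

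**What to change.** 1. **SAP 5.4.** Replace the sentence that derives the rule from the protocol, for example: *The protocol specifies last value carried forward during hospitalization. From SAP version 1.4, adopted after the primary manuscript was drafted, the primary analysis scores every hospital day as positive; this is the statistical team's interpretation.*
2. **SAP 7.2.1.** Commit to one sensitivity analysis that repeats the age-stratified log-rank test with hospital days taking the last pre-admission result, negative as well as positive. State the confirmation convention as an assumption, not as protocol text. It could be that a carried-forward negative confirms, or that hospital days count as no result under the SAP 5.4 gap rule.
3. **Results.** Note the modification explicitly, with its timing, as Protocol 6.0 requires. Report by arm how many participants' time or event status differs between the rules.

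The cost is a few sentences, one rerun of the log-rank test and one count by arm. No new data are needed, and the primary analysis stays as it is.

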7.2.1 Additional Analyses of Primary Outcome

A sensitivity analysis will right-censor follow-up on the day of hospital admission. These two analyses (primary and sensitivity) represent the range of plausible scenarios for shedding during hospitalization under the assumption that any association between hospitalization and shedding must be positive; i.e., conditional on past history, the risk of viral shedding on any given day is at least as large for hospitalized as for non-hospitalized subjects. It is expected that a relatively modest proportion of subjects will be hospitalized, limiting the impact of assumptions concerning shedding during hospitalizations on the primary analysis. Additional sensitivity analyses, including analyses in which the end date of shedding is modeled as a latent variable will be considered.

Quantification of the magnitude of “treatment effect,” and indeed the interpretation of the trial results, will depend on the specific patterns of the shedding duration distribution. For example, in the unexpected scenario where the cumulative incidence curves for the ending of shedding actually cross during the $(DayR + 1)$ to $(DayR + 14)$ evaluation period, the treatment arm with lower 14-day shedding rate would likely be preferred regardless of any shorter-term benefit observed in the other arm. Assuming, however, that the assumption of proportional hazards is found to be consistent with the data, the effect of the treatment will be expressed as a hazard ratio with 95% confidence interval. We will also report the randomization age-group-stratified differences between the randomized groups in truncated mean shedding duration to 14 days and in median shedding duration with 95% confidence intervals based on estimates derived from Kaplan-Meier curves. The confidence intervals for each difference will be derived by first sampling with replacement the participant-level data from among the participants with at least some viral-shedding information, then fitting the stratified Kaplan-Meier curves, and finally estimating stratum-specific and overall median shedding durations and truncated mean durations. This will be repeated for a minimum of 500 bootstrap replicates. The 2.5th and 97.5th percentiles of each difference between treatments, overall and by age group randomization stratum, will be used as the confidence interval endpoints. The confidence interval construction is similar to the approach taken in Calkins et al.[7] for overall and stratified confidence intervals of the restricted mean duration, with a key difference being that no weights will be applied because treatment groups were randomly assigned.

As an additional exploratory analysis of the primary outcome, the primary analysis will be repeated when stratifying by duration of pre-randomization symptoms rather than by age group.

